3.2.2 Nivolumab Pharmacokinetics

The PK of single-dose nivolumab was assessed in patients with multiple tumor types in the CA209001 trial, using a dose range of 0.3 to 10 mg/kg. The time of maximum concentration observed (Tmax) across single dose levels ranged from 1.6-3.0 hours with individual values ranging from 0.9 to 7.0 hours. Nivolumab has a linear PK in the range of 0.3 to 10 mg/kg with dose- proportional increase in the maximum concentration observed and in the area under the curve from zero to infinity, with low to moderate inter-subject variability observed at each dose level, i.e., a coefficient of variation ranging from 7%-45%. The geometric mean clearance after a single IV dose of nivolumab ranges from 0.13-0.19 mL/h/kg, whereas the mean volume of distribution ranges from 83-113 mL/kg across doses. The mean terminal half-life of nivolumab is 17-25 days, which is in accordance with the half-life of endogenous IgG4 antibodies, indicating that they share a similar elimination mechanism. The elimination and distribution of nivolumab is dose-independent in the dose ranges studied.

The PK of multiple nivolumab doses is being investigated in the CA209003 trial. A preliminary population pharmacokinetic model has been developed using nonlinear mixed effect modeling using data from 350 patients accrued in the CA209001, CA209002, and CA209003 trials. Dosing based on normalizing by body weight produces relatively constant trough concentrations over a wide range of body weights, and is therefore appropriate for trials of nivolumab.

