Treatment interruption and administration of corticosteroids were used to manage hepatic or gastrointestinal AEs, which overall were fully reversible. Hormone replacement therapy was used to manage endocrine AEs. Several patients with these AEs successfully restarted nivolumab therapy. Drug-related pneumonitis was noted in 3% of patients. Grade ≥ 3 pneumonitis developed in only 3 patients (1%). There was no clear relationship between the occurrence of pneumonitis and dose level, dose number, or tumor type. Low-grade pneumonitis generally resolved with discontinuation of treatment and administration of corticosteroids. Infliximab and/or mycophenolate were used as additional immunosuppressants in 3 patients, but it remains uncertain whether this provided additional benefit. Three drug-related deaths (1%) due to pneumonitis were noted. In two of these cases, early and aggressive intervention such as systemic corticosteroid therapy was not initiated, and this likely significantly contributed to the fatal event, whereas in the 3rd patient, concomitant administration of other anti-cancer agents (erlotinib and vinorelbine) may have aggravated toxicity.

In the CheckMate 025 study using the now established nivolumab dose of 3 mg/kg every 2 weeks, following a median duration of treatment of 5.5 months (range, <0.1 to 29.6), treatment-related AEs of any grade occurred in 319/406 patients (79%). The most frequent treatment-related AEs were fatigue (33%), nausea (14%), and pruritus (14%). Grade 3/4 treatment-related AEs occurred in 19% of patients, with the most common Grade 3/4 AE being fatigue (2%). Treatment-related AEs leading to nivolumab discontinuation were noted in 8% of patients. There were no nivolumab-related deaths.⁹

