5.3 Study Design and Duration

This is a phase I-II dose-finding trial to determine the optimal dose of the targeted oral agent MGCD516 when combined with immunotherapy via intravenous Nivolumab at fixed dose 240 mg IV every 2 weeks, in patients with metastatic renal cell carcinoma with a clear cell component who have progressed following treatment with anti-VEGF agents. The goal of the study is to determine an optimal oral MGCD516 dose level among the four levels 60, 80, 120

Proprietary of MD Anderson Cancer Center

and 150 mg/day given orally daily until toxicity or progressive disease. Dose-finding will be done using the sequentially adaptive phase I-II late-onset EffTox (Lo-EffTox) trade-off-based design of Jin et al.⁶⁰⁻⁶² To determine the optimum dosage, efficacy is defined as achieving complete response (CR), partial response (PR), or stable disease (SD) within 6 weeks, and the occurrence of any of the following toxicities within 12 weeks from the start of therapy will be considered a dose-limiting **toxicity** (DLT), if judged by the Investigator to be clinically relevant and related (possibly or probably) to administration of either or both study drug(s):

- Hematologic DLTs:
 - Grade ≥ 3 febrile neutropenia ($ANC < 1.0 \times 10^9/L$ with either a single temperature $\geq 38.3^{\circ}C$ or a sustained temperature of $\geq 38^{\circ}C$ for more than 1 hour)
 - Grade 3 thrombocytopenia (platelets $< 50.0 \times 10^9/L \geq 25.0 \times 10^9/L$) if associated with:
 - A bleeding event that requires an elective platelet transfusion, OR
 - A life-threatening bleeding event which results in urgent intervention and admission to an Intensive Care Unit
 - Grade 4 thrombocytopenia (platelets $< 25.0 \times 10^9/L$)
- Non- Hematologic DLTs:
 - Any Grade 4 non-hematological toxicity
 - Grade ≥ 2 drug-related uveitis that does not respond to topical therapy OR requires systemic treatment
 - Grade 3 overlapping toxicities of nivolumab and MGCD516, including diarrhea, rash, fatigue, or elevation of serum amylase/lipase, lasting > 3 days despite optimal supportive care with the exception of:
 - Grade 3 fatigue lasting ≤ 5 days
 - Grade 3 rash that resolves to \leq Grade 1 within 3 weeks
 - Grade 3/4 elevation in serum amylase and/or lipase that are not associated with clinical or radiological evidence of pancreatitis
 - Any other Grade 3 non-hematologic toxicity lasting > 3 days despite optimal supportive care with the exception of:

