13.0 SAFETY ASSESSMENTS AND REPORTING REQUIREMENTS

13.1 All patients will be evaluated for safety. The safety parameters include all laboratory tests and hematological abnormalities, physical examination findings, and spontaneous reports of adverse events reported to the investigator by patients. An adverse event is any untoward or unfavorable medical occurrence in a human subject, including any abnormal sign (for example, abnormal physical exam or laboratory finding), symptom, or disease, temporally associated with the subject's participation in the research, whether or not considered related to the subject's participation in the research. All adverse events encountered after the patient has provided informed consent and until 4 weeks after the patient has stopped treatment will be evaluated according to the NCI Common Toxicity Criteria (CTCAE) version 4.0. Prior treatment associated toxicities present at the time of informed consent but before study treatment initiation, will be recorded as baseline abnormalities and graded according to NCI CTCAE version 4.0 criteria.

Information about all adverse events, whether volunteered by the subject, discovered by investigator questioning, or detected through physical examination, laboratory test or other means, will be collected and reported as described in the data submission schedule

**Reporting Responsibilities of Investigators under 21 CFR 312.64(b) and
Sponsors under 21 CFR 312.32(c)(1)(i) for Serious and Unexpected Suspected**

Proprietary of MD Anderson Cancer Center

Adverse Reactions

Term	Investigator Responsibility	Sponsor Responsibility	Final Determination Responsibility
Serious (or life-threatening)	Yes (Investigator must report all serious adverse events to the sponsor immediately)	Yes	An event is considered serious or life-threatening, based on either the investigator's or sponsor's opinion.
Unexpected	No (No requirement to assess "expectedness")	Yes	The sponsor is responsible for determining whether event meets the definition of "unexpected," based on whether the event is listed in the investigator brochure; or if an investigator brochure is not required or available, is not consistent with the risk information described elsewhere in the general investigational plan or elsewhere in the current application.

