- Unless otherwise noted, the electronic SAE application (eSAE) will be utilized for safety reporting to the IND Office and MDACC IRB.
- Serious adverse events will be captured from the time of the first protocol-specific intervention, until 30 days after the last dose of drug, unless the participant withdraws consent. Serious adverse events must be followed until clinical recovery is complete and laboratory tests have returned to baseline, progression of the event has stabilized, or there has been acceptable resolution of the event.

Proprietary of MD Anderson Cancer Center

- Additionally, any serious adverse events that occur after the 30 day time period that are related to the study treatment must be reported to the IND Office. This may include the development of a secondary malignancy.

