14.0 STATISTICAL CONSIDERATIONS / DATA ANALYSIS

14.1 Phase I-II Dose-Finding Design

This is a phase I-II dose-finding trial to determine the optimal dose of the targeted oral agent MGCD516 when combined with immunotherapy via Nivolumab at fixed dose 240 mg IV every 2 weeks, in patients with metastatic renal cell carcinoma with clear cell component who have had prior treatment with anti-VEGF agents. The scientific goal of the trial is to determine an optimal MGCD516 dose level among the four levels **60, 80, 120, 150** mg/day given orally each day until toxicity of progressive disease. Dose-finding will be done using the sequentially adaptive phase I-II late-onset EffTox (Lo-EffTox) trade-off-based design of Jin et al.⁶⁰⁻⁶² For the goal of determining an optimum dose, dose limiting Toxicity within 12 weeks from the start of therapy is defined as described in section 5.3, and Efficacy is defined as achieving CR, PR, or stable disease within 6 weeks. Patients who have received at least 6 infusions of nivolumab 240 mg IV every 2 weeks with no DLTs related to nivolumab, will have the option to transition to the equivalent nivolumab schedule of 480 mg IV every 4 weeks. Because such a change will occur after at least 12 weeks from study initiation the endpoints are not affected for the purpose of dose escalation and de-escalation.

[figure not shown]
Each cohort will include no more or less than 3 patients. A maximum of 60 patients will be treated in up to 20 cohorts of size 3, with the first cohort treated at **80** mg/day, all successive

Proprietary of MD Anderson Cancer Center

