doses chosen by the Lo-EffTox method, and no untried dose level skipped when escalating. Enrollment will continue without delay except, we also require at least one patient's toxicity outcome to have been observed at the current dose (which takes a maximum of 12 weeks) before enrolling the next cohort of patients. For the two Lo-EffTox dose acceptability rules, the upper limit on the probability of toxicity is .40, the minimum probability of Efficacy .50, and cut-offs .10 will be used for both stopping probability criteria. If the lowest dose level is found to be unacceptable in terms of either high toxicity or low efficacy, the trial will be terminated and no dose level will be selected. The three equivalent trade-off probability pairs used for computing the trade-off contours are (.50, 0), (.70, .25), (1, .65). The prior hyper-parameters were computed based on the assumed prior means $\text{Prob}(\text{Efficacy} | \text{dose}) = .25, .30, .35, .50$ and $\text{Prob}(\text{Toxicity} | \text{dose}) = .20, .25, .30, .40$, respectively, at the four MGCD-516 dose levels. The overall prior effective sample size = 1.

The Lo-EffTox design will be implemented using the specialized computer program developed by Jin et al.⁶⁰ The study biostatistician [name], [name], or [name] in the Biostatistics Department should be consulted as necessary during trial conduct. Secondary outcomes will include progression-free survival (PFS) time, overall survival (OS) time, objective response rate (ORR), and quality of life (QOL). Unadjusted distributions of the time-to-event outcomes will be estimated using the method of Kaplan and Meier⁶⁸ and their relationship to prognostic covariates will be evaluated by Bayesian piecewise exponential survival regression.⁶⁹

A Toxicity/Efficacy Summary will be submitted to IND Office Medical Monitor; every three patients, after the first twelve weeks of study therapy or administration is discontinued, whichever comes first, until 60 patients have completed study therapy.

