14.2 Design Operating Characteristics

Operating characteristics of the design are summarized below, based on simulations with 1000 replications per scenario. In the simulations, it is assumed that the times to toxicity and efficacy follow Weibull distributions, the percentage of toxicity (or efficacy) events occurring in the later half of each evaluation interval is 50%, and the accrual rate is 2 cohorts per month.

Scenario		Dose (mg/day)					
		60	80	120	150	None	
1							
	True pT, pE	.20, .25	.30, .45	.40, .70	.50, .95	-	
	Trade-off Value	-0.83	-0.58	-0.24	0.12	-	
	% selected	0	11.5	41.0	41.0	6.5	
	# Patients Treated	3.5	8.7	18.8	27.6	-	
2							
	True pT, pE	.20, .40	.30, .65	.60, .70	.90, .75	-	
	Trade-off Value	-0.53	-0.18	-0.55	-0.91	-	
	% selected	8.4	75.5	1.4	0	14.7	
	# Patients Treated	8.0	31.1	10.6	6.2	-	
3							
	True pT, pE	.30, .65	.60, .72	.65, .75	.70, .78	-	
	Trade-off Value	-0.18	-0.51	-0.52	-0.54	-	
	% selected	78.4	10.3	0.1	0	11.2	
	# Patients Treated	27.5	18.5	6.8	3.9	-	
4							
	True pT, pE	.10, .15	.15, .20	.20, .25	.25, .30	-	
	Trade-off Value	-0.87	-0.85	-0.83	-0.81	-	
	% selected	0	0	0	3.8	96.2	
	# Patients Treated	3.2	3.3	4.3	22.2	-	
5							
	True pT, pE	.50, .25	.60, .35	.70, .45	.80, .56	-	
	Trade-off Value	-1.30	-1.26	-1.21	-1.14	-	

% selected	0	0	0	0	100
# Patients Treated	4.2	6.2	4.9	5.4	-

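### Adverse-event evaluation can end before the 12-week DLT window closes for patients who stop both agents before week 8 without a DLT

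*Combined protocol and SAP*

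**What the plan says.** **Endpoint.** Section 14.1 states that "dose limiting Toxicity within 12 weeks from the start of therapy is defined as described in section 5.3". Section 5.3 counts an event only if the investigator judges it clinically relevant and at least possibly related to either drug. The primary objective in section 2.0 uses the same 12 weeks. Nothing in these sections limits the window to time on treatment.

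**Adverse-event evaluation.** Under section 13.1, "All adverse events encountered after the patient has provided informed consent and until 4 weeks after the patient has stopped treatment" are evaluated by CTCAE 4.0. The last scheduled assessment is the end-of-treatment evaluation (section 10.7 and the study calendar). Later follow-up is for survival (section 10.8).

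**Partial cover.** Section 13.2 captures serious events to 30 days after the last dose; beyond that, "any serious adverse events that occur after the 30 day time period that are related to the study treatment must be reported". Section 8.0 requires weekly follow-up of a suspected-related event that led to an interruption or stop. Sections 6.4 and 8.0 allow one agent to continue when the other is stopped.

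**Use in dose-finding.** Section 14.1 calls for a "toxicity outcome to have been observed at the current dose (which takes a maximum of 12 weeks) before enrolling the next cohort of patients"; a single patient's result suffices. The toxicity and efficacy summary falls due at twelve weeks, or at discontinuation if that is sooner.

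**Imaging.** Section 10.4 ties scheduled scans to being on protocol therapy. Section 10.7 asks for imaging at a toxicity stop only if the stop precedes restaging.

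**The concern.** DLT status at 12 weeks is the toxicity input to Lo-EffTox, so ascertainment should cover the same 12 weeks for every patient. The first scan is at week 6, so a stop for progression about then is foreseeable, and 4 weeks of further grading reaches only week 10. The provisions that outlast section 13.1 leave a gap: section 13.2 covers related serious events, and section 8.0 covers the event that caused the stop. A new, related, non-serious Grade 3 event, such as a laboratory abnormality persisting beyond a week or prolonged fatigue, could meet section 5.3 and have no planned route into the data.

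Late related events are plausible: "The mean terminal half-life of nivolumab is 17-25 days", so 28 days is less than two half-lives. At stake is completeness of a primary endpoint that feeds the .40 toxicity limit and the trade-off between doses.

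A smaller, parallel gap affects PFS. After a toxicity stop without progression, no scan schedule continues, although section 11.6 runs PFS to progression or death.

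**Working it through.** **Check on the design inputs.** The trade-off values in section 14.2 can be recomputed from the contour points in section 14.1 as 1 − [((1 − pE)/0.5)^r + (pT/0.65)^r]^(1/r), with r = 0.977 solved from (.70, .25). All 20 values agree within 0.01. The steps below do not depend on them.

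**1. Uncovered time.** Adverse events: 12 − 4 = 8, so there is a gap only for stops before week 8, of length 8 − stop week. This gives 6 weeks for a stop at week 2, 4 at week 4, 2 at week 6, 1 at week 7 and 0 from week 8. For the 30-day serious-event window the threshold is 12 − 30/7 = 7.7 weeks. If either agent continues to week 8 there is no gap.

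**2. Share of 12-week DLTs after evaluation ends.** Section 14.2 assumes Weibull times and that "the percentage of toxicity (or efficacy) events occurring in the later half of each evaluation interval is 50" per cent. Set F(12) = p and F(6) = p/2. For p from .20 to .50, the share 1 − F(stop + 4)/p is about 50% for a stop at week 2, 32–33% at week 4, 15–16% at week 6 and 8% at week 7.

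**3. Risk per week-6 stopper, upper figure.** For a patient DLT-free at week 6 and evaluated to week 10, the risk is [p − F(10)]/[1 − F(6)].

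| p | Weibull shape | Risk in weeks 10–12 |
|---|---|---|
| .25 | 1.107 | .0463 |
| .30 | 1.134 | .0567 |
| .40 | 1.195 | .0789 |

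This keeps the on-drug hazard after both drugs have stopped, so it is high.

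**4. Risk with a nivolumab-only hazard.** From section 3.2.3.1: "Grade 3/4 treatment-related AEs occurred in 19% of patients", over a median 5.5 months (23.9 weeks) of treatment. Assuming a constant hazard, −ln(1 − .19)/23.9 = .0088 per week, and the two-week risk is 1 − exp(−2 × .0088) = .017. This counts every Grade 3/4 related event, several of which section 5.3 excludes.

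**5. Drug remaining at 28 days.** Nivolumab: 28/25 = 1.12 to 28/17 = 1.65 half-lives, leaving 46% to 32%. MGCD516 (half-life 40–53 hours, section 3.1.3.1): 672/53 = 12.7 to 672/40 = 16.8 half-lives, so essentially none. Step 4 is therefore the more relevant figure.

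**6. Possible consequence.** Two illustrations:

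- Suppose a share f stopped at week 6 and were scored DLT-free, which the protocol does not say. Apparent toxicity is p(1 − f) + f·F(10). With p = .40 and F(10) = .337, f = .12 gives .352 + .040 = .392, and f = .24 gives .304 + .081 = .385.
- Using independent Beta(1,1) priors rather than the Lo-EffTox model, and the DLT counts in section 3.4, one added DLT moves Pr(toxicity < .40) from .83 to .67 at 80 mg (4/15 to 5/15) and from .41 to .27 at 120 mg (10/24 to 11/24). All stay above the .10 cut-off.

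**The case against.** **Section 13.1 is not exclusive.** It says how events in that period are graded, not that collection then ceases. It also points to a data submission schedule that is not in the documents, and the specific endpoint definition could be held to govern. That leaves room for good practice at the site, but no scheduled assessment or stated rule carries non-serious events to week 12.

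**Late events say little about dose.** MGCD516 is gone by then, and nivolumab is given identically in every cohort. This largely stands. It is why the on-drug range is only an upper figure and why distortion of the dose comparison is unlikely.

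**Lo-EffTox is built for delayed outcomes.** The reference cited in section 14.1 describes data augmentation for that purpose, so partial follow-up would probably enter as such. A reader might infer that early stoppers are counted as DLT-free; the documents do not say so.

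**How many patients?** A reader might add the 5 without disease control (42 − 37) to the 4 adverse-event stops and treat about 9 of 42 as early stoppers. No stop dates support this. Treatment beyond progression is allowed (section 8.3), the adverse-event stops span the whole course, and any patient among the 17 with a recorded DLT (4 + 10 + 3) already has an outcome.

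**Withdrawal wording.** Section 8.0 couples some treatment stops to study withdrawal, and section 12.0 ends data collection at withdrawal. A reader might infer that survival follow-up was lost. Sections 8.2 and 10.8 point the other way. Section 3.4 reports 34 of 42 alive with 12 on treatment, so at least 34 − 12 = 22 patients off treatment had known status. This suggests the wording was not applied literally, and no OS bias is shown.

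**PFS.** Section 6.1.3 requires return visits while progression-free. It sets no scan schedule, so the imaging point survives, but section 3.4 reports only 4/42 adverse-event stops.

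**Conclusion.** The mismatch is real on the text: adverse-event evaluation does not cover the full 12-week DLT window for a patient who stops both agents before week 8 without a DLT. The week-8 threshold is exact arithmetic.

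The effect is probably small. Per week-6 stopper, the chance of a DLT in the uncovered two weeks is about 1.7%, assuming a constant nivolumab-only hazard, and 4.6–7.9% at most, assuming the on-drug Weibull hazard persists. For every ten such patients that is 0.17 to 0.79 expected DLTs. Earlier stops leave a longer gap. The number of such patients is unknown and may be zero. No missed DLT is shown, and nothing supports a claim that the .40 rule would have acted differently or that another dose would have been chosen. The point merits attention because it concerns a primary endpoint and is cheap to close, not because it undermines the design.

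**What to change.** **Section 13.1:** collect and grade adverse events until the later of 12 weeks from first dose or 4 weeks after last dose, regardless of treatment status. For any further early stopper this costs at most a few weeks of telephone or record-review follow-up.

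**Patients already enrolled (42 by February 2020):** this is the main practical step. Identify those who stopped both agents before week 8, check their records for DLTs to week 12, and report by dose how many had under 12 weeks of DLT follow-up. The cost is a record check in a small trial.

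**Section 10.4 (secondary):** after a toxicity stop without progression, continue scheduled scans to progression or new anticancer therapy. The cost is a few extra scans.

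**Sections 8.0 and 12.0 (clarification only):** separate stopping therapy from withdrawing from the study, and limit the end of data collection to patients who withdraw consent for follow-up, in line with sections 8.2 and 10.8. This takes a few sentences.

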13.2 Serious Adverse Event Reporting (SAE)

An adverse event or suspected adverse event reaction is considered "serious" if, in the view of either the investigator or the sponsor, it results in any of the following

Proprietary of MD Anderson Cancer Center

outcomes:

- Death
- A life-threatening adverse drug experience – any adverse experience that places the patient, in the view of the initial reporter, at immediate risk of death from the adverse experience as it occurred. It does not include experience that, had it occurred in a more severe form, might have caused death.
- Inpatient hospitalized or prolongation of existing hospitalization.
- A persistent or significant incapacity or substantial disruption of the ability to conduct normal life functions.
- A congenital anomaly/birth defect.

Important medical events that may not result in death, be life-threatening, or require hospitalization may be considered a serious adverse drug experience when based upon appropriate medical judgment, they may jeopardize the patient or subject and may require medical or surgical intervention to prevent one of the outcomes listed in this definition. Examples of such medical events include allergic bronchospasm requiring intensive treatment in an emergency room or at home, blood dyscrasias or convulsions that do not result in inpatient hospitalization, or the development of drug dependency or drug abuse (21 CFR 312.32).

- Important medical events as defined above, may also be considered serious adverse events. Any important medical event can and should be reported as an SAE if deemed appropriate by the Principal Investigator or the IND Sponsor, IND Office.
- All events occurring during the conduct of a protocol and meeting the definition of a SAE must be reported to the IRB in accordance with the timeframes and procedures outlined in “The University of Texas M. D. Anderson Cancer Center Institutional Review Board Policy for Investigators on Reporting Unanticipated Adverse Events for Drugs and Devices”. Unless stated otherwise in the protocol, all SAEs, expected or unexpected, must be reported to the IND Office, regardless of attribution (within 5 working days of knowledge of the event).
- All life-threatening or fatal events, that are unexpected, and related to the study drug, must have a written report submitted within 24 hours (next working day) of knowledge of the event to the Safety Project Manager in the IND Office.
- Unless otherwise noted, the electronic SAE application (eSAE) will be utilized for safety reporting to the IND Office and MDACC IRB.
- Serious adverse events will be captured from the time of the first protocol-specific intervention, until 30 days after the last dose of drug, unless the participant withdraws consent. Serious adverse events must be followed until clinical recovery is complete and laboratory tests have returned to baseline, progression of the event has stabilized, or there has been acceptable resolution of the event.

Proprietary of MD Anderson Cancer Center

- Additionally, any serious adverse events that occur after the 30 day time period that are related to the study treatment must be reported to the IND Office. This may include the development of a secondary malignancy.

